Feasibility and acceptability of six-weeks of high intensity interval training in wheelchair users with SCI

Short Title: HIIT in Spinal Cord Injury (HIIT-SCI)

Principal Investigator: [name], RET
Human Engineering Research Laboratories
VA Pittsburgh HealthCare System
University of Pittsburgh
[name]
[name]
[contact]

Funded By: University of Alabama – Birmingham
[name]
[name]
[contact]

Eunice Kennedy Shriver National Institute of Child Health and
Human Development (NICHD)
NIH Clinical Center
[name]
[name]

Study Protocol Number: NCT03152110 (National Clinical Trials)
PRO17020277 (OSIRIS)
STUDY19040142 (University of Pittsburgh)

Overview

An upper extremity form of high intensity interval training (HIIT) that is effective, safe, quick and has acceptable positive affect could be an attractive option for persons with SCI who are not presently exercising and have low fitness levels. The study will look at feasibility and acceptability of a 6-week HIIT program for persons with a spinal cord injury/dysfunction who are untrained. Additionally, the study will look at the effects of the training program on changes in activity levels. Participants will complete a 6-week HIIT training program in their homes, as well as two laboratory visits where aerobic and anaerobic fitness will be measured.

Research Activities and Consent

Potential subjects who contact the Human Engineering Research Laboratories (HERL) and express an interest in the study will undergo a brief telephone screening. The telephone screening will be used to provide the potential subject with more information and allow them to ask questions regarding the research study to help them determine their interest in participating. During the phone screening, we will ask them basic questions to see if they might qualify for the study. These questions will be based on the inclusion/exclusion criteria for the study, as well as questions about their current lifestyle. Prior to asking the participants these questions, we will make sure they understand why we are asking these questions and obtain their permission to do so. We will note the date and time of the permission obtained. We will use the Exercise Stages of Change Questionnaire, as well as questions about their current fitness activities to assess eligibility for the study. We want to make every effort to determine whether or not a participant would potentially qualify for the study prior to contacting their Primary Care Physician (PCP).

Obtaining the approval of a physician is highly recommended for anyone starting an exercise program, regardless of disability. We will rely on the potential subject's PCP in order to assess their readiness to participate in the research study. A participant's PCP will know their medical history, and will be able to evaluate their overall health. The physician's release form will detail the study and list all contraindications. In addition, the PCP may contact the study team should he/she need additional information prior to signing the release form. The study team will not access any medical records. “

Location of testing: (1) two in-lab visits at University of Pittsburgh, Endocrinology and Metabolism Research Lab (Montefiore Hospital); (2) subjects' homes or an agreed upon location where it's safe to store exercise equipment and for our research staff; (3) if necessary, there may be a visit at the Human Engineering Research Laboratories or a safe, agreed upon location for the purposes of retrofitting the add-on hand bike (this is detailed further below).

A subject who contacts HERL over the phone will be asked for their verbal consent to the screening procedure. The screening procedure will include asking the participant the inclusion/exclusion criteria. The screening procedure will also determine which training options are available for them (i.e., handcycle and/or add-on hand bike). For example, if a person meets all the inclusion/exclusion criteria and they weigh less than 250 lbs, they will have the option to train using a handcycle or an

add-on hand bike. If a person meets all the inclusion/exclusion criteria and they weigh more than 250 lbs, they will have the option to train using the add-on hand bike or not to participate. If the add-on hand bike option is selected, they will be asked to report the make/model of their wheelchair for retrofitting purposes. The study team feels that wheelchair make/model is sufficient information to determine whether the add-on hand bike can be retrofitted; however, an additional in-person visit may be scheduled for fitting purposes.

If the participant is eligible and would like to participate, the study team will send a physician release form to be signed directly by the physician (please see “Cover Letter for Physician Release” and “PCP Release” under the “Supporting Documentation” section). After the study team receives the signed release form, the participant will be scheduled for their Visit 1, Baseline Visit. Participants will be given the following instructions prior to their first lab visit:

1. Do not participate in any strenuous physical activity 24 hours prior to testing.
2. Do not eat a large meal 4 hours prior to testing, however a light snack is okay.
3. Do not drink alcohol or caffeine 4 hours prior to testing.
4. No smoking 1 hour prior to testing.
5. Wear comfortable, loose clothing that allows you to move your arms freely and that you can easily exercise in.

Visit 1: Baseline Visit

Eligible participants will be directed to come to the Endocrinology and Metabolism Research Lab to obtain written informed consent, complete study questionnaires, and perform baseline exercise tests. Participants will be considered enrolled in the study after they have signed the informed consent document.

Participants will complete the following questionnaires regarding demographics, pain and health measures, general health and function, and physical activity:

(1) Demographics questionnaire: May include information such as disability type, level of SCI, years with disability, age, gender, and information about their wheelchair (e.g. make, model, cushion, etc.).

(2) Numerical Rating Scale (NRS): Participants will complete this scale once for each upper limb joint (wrist, elbow and shoulder). Participants will be asked to rate their average, most severe, and least severe wrist, elbow and shoulder pain during the last 24 hours using an 11 point scale (i.e. 0-10) anchored at the ends by "no pain" and "worst pain ever experienced." An 11 point NRS measure of intensity allows for comparison across clinical trials of pain treatment and is recommended as a core outcome measure for chronic pain clinical trials. NRS pain measures are widely used and have been shown to be valid and reliable assessments of pain.

(3) Wheelchair Users Shoulder Pain Index (WUSPI): The WUSPI is a 15 item, self-report instrument that measures shoulder pain intensity, within the last week, in wheelchair users during various functional activities of daily living such as transfers, leading a wheelchair into a car, wheelchair mobility, dressing, bathing, overhead lifting, driving, performing household chores and sleeping. The WUSPI is a valid and reliable measure of shoulder pain. Test-retest reliability of the total index score was 0.99 and Cronbach's alpha (internal consistency) was 0.98.

(4) Short Form Health Survey Walk Wheel (SF-36 WW): A 36-item general health and function questionnaire that has been validated for persons with SCI/D. The SF-36 is a brief, multi-dimensional, self-report health questionnaire that measures eight concepts: physical functioning, role limitation due to physical problems, bodily pain, general perception of health, vitality, social function, role limitation due to emotional problems and mental health.

(5) Physical Activity Scale for Individuals with Physical Disabilities (PASIPD): The PASIPD is a 13-item self-report instrument covering (1) leisure activities, (2) household activities, (3) occupational activities and (4) light, moderate, and strenuous sport and recreational activities. The scale asks individuals to report how many days and hours per week that they spend participating in these various physical activities and a total score is calculated that is expressed in a metabolic equivalent (MET). The maximum possible score on the PASIPD total score is 199.5 MET.

(6) Physical Activity Stages of Change: This is a brief, 5-item, yes/no questionnaire that assesses an individual's readiness to exercise.

(7) Exercise Participation Evaluation: This is a 4-item questionnaire developed by our study team that will be used to determine if the participant exercises, and if so, what type of exercise and how frequent.

(8) Profile Of Mood States (POMS): This is a validated questionnaire that contains a series of descriptive words/statements that describes feelings. The participant will self-report on each of these areas using a 5-point Likert scale to assess total mood disturbance.

Lastly, height and weight will be taken. Subjects will transfer to a mat table where they will lay on their backs. Once in this position we will measure their height with a measuring tape. Weight will be measured using a wheelchair scale. Participants will be weighed with their wheelchair and the wheelchair will be weighed without the subjects in them. The weight will be the difference between the two measurements.

Following completion of all study questionnaires, participants will begin exercise testing. Both exercise tests will be administered by an exercise physiologist and directly supervised by a physician.

Both tests have been widely used in previous research studies. The tests are outlined in further detail below:

(1) Maximal aerobic exercise test: the purpose of this test is to evaluate cardiac function and fitness. Additionally, this test will determine peak power output (PPO) which will later be used to set an individualized goal for the participant during the HIIT protocol to be completed in the second, and possible third and fourth visits. Prior to starting the test, participants will be fitted with a mask that analyzes the air that is being inhaled and exhaled (also known as "open circuit spirometry"). Cardiorespiratory measures (i.e., heart rate, blood pressure, oxygen consumption, respiratory exchange ratio, pulmonary ventilation, carbon dioxide expiration, etc.) will be recorded throughout this test. A heart rate monitor will be worn around the chest. Participants will be able to use a private space to put on the heart rate monitor. A member of the study team will verify the heart rate monitor is placed properly.

Prior to beginning the test, the Borg and Wheel scales will be explained to participants (please see "Borg Scale" and "Wheel Scale" under the "Supporting Documentation" section). Ratings of

Perceived Exertion (RPE) scales (such as the Borg and Wheel scales) rate how hard a person feels their body is working and is an accepted supplementary tool for exercise programs. Throughout the test, the participant will be asked to report their RPE by pointing to the corresponding number on the scale. The exercise test will be administered using an incremental, modified protocol on an electronically-braked arm ergometer. A study team member will choose one of two exercise protocols, depending on the answers to the questions on the demographics questionnaire.

For one protocol, the resistance will initially be set at 10W and will increase by 10W every minute until the participant can no longer continue, or until their respiratory exchange ratio exceeds 1.15. For the second protocol, the resistance will initially be set at 35W and will increase by 10W every minute until the participant can no longer continue, or until their respiratory exchange ratio exceeds 1.15. Both protocols will ask the participant to maintain an RPM of 55-65 revolutions per minute (RPM). If the RPMs drop below 55 for more than 20 seconds, the test will be completed.

(2) Maximum power output test: the primary purpose of this test is to evaluate the highest amount of power that the participant can produce in a short period of time. Other measures include heart rate, blood pressure, relative peak power, anaerobic capacity and anaerobic fatigue. The same ergometer will be used for this study that was used for the maximal aerobic exercise test. Initially, the resistance will be set at zero and will then be increased over the duration of the test. The actual test will last one minute in duration. For the first 30 seconds, the participant will crank on the cycle with minimal resistance. Then, the resistance will be increased to a maximal level and participants will crank as hard and as fast as they are able to for the last 30 seconds. After that the test is completed, the resistance will then return to zero and the participants will cycle at a comfortable pace to cool down.

Participants will rest a minimum of 20 minutes in between each assessment.

Following completion of the exercise tests, the study team will introduce the participant to the type of exercises that will be performed for the study. They will be able to use the ergometer in the lab to try out a brief HIIT protocol.

Activity Monitor Data Collection

Activity monitors will be given to participants to address aim 5 as equipment is available. The following study procedures will not be performed if the monitors are not available. The following procedures will be followed when monitors are available and activity data is going to be collected.

After the participants are introduced to the training, they will be given the two activities monitors that will be used to look at activity for the duration of the study. A SensorTag gyroscope will be secured to the participants wheelchair wheel in a position where it will not affect propulsion. This sensor will remain on the wheel for the duration of the study. Participants will also be given an ActiGraph GT9X accelerometer. This sensor will be worn on the wrist like a watch. The subject will be shown how to use the activity monitors (including donning/doffing, and operation), and provide ample time for practice. The subject will be asked to demonstrate how to use the devices to ensure compliance. Participants will be instructed to wear the activity monitor at all times as tolerated, including sleeping, or most of time, except for showering/bathing and swimming. Participants will be given instructions and details on how to use/wear the monitors.

At the regularly scheduled training visits, the trainer will monitor the function of the monitors. They will download data and replace sensor batteries as needed.

The baseline period of activity collection will be the time after the first study visit at Montefiore hospital until the first in-home training session occurs.

Visit 1 will take up to 3 hours to complete.

6-Week HIIT Protocol:

If the participant already owns a handcycle, we will make every attempt to fit their handcycle to the roller system that will be used for the study. If we are not able to retrofit their handcycle or if they do not own a handcycle, the study team will provide a handcycle for the duration of the program. If a participant is unable to transfer into the handcycle, then the study team will provide assistance and tips for how to get in and out. If a participant is still uncomfortable with transferring into the handcycle, then they may be provided with an add-on hand bike, or they have the option to not participate in the study. At the end of the study, the handcycle/hand bike and the roller system will be returned to the study team. Participants will be given a heart rate monitor, which they will be asked to wear and use for every exercise session for the duration of the study. They do not have to return the heart rate monitor at the end of the study. Participants will be provided with a bike computer that will be fit to the handcycle/hand bike and will be used solely for the purpose of recording power output and heart rate during the exercise sessions. Participants must return the bike computer at the end of the study.

The first exercise visit will be tentatively scheduled within one week of the first study visit. Exercise sessions will be scheduled, ideally, 3 times per week (every other weekday), with the total training protocol lasting 6 weeks. Two of the sessions will be supervised by a trainer and one session will be completed on their own. The trainer may go to the third session if the participant requests assistance getting in and out of the handcycle or attaching the add-on hand bike, however, they will not provide any coaching or verbal cues during exercise. During the last week (week 6), subjects can opt to have their supervised sessions via FaceTime or Skype (if they have a smartphone or computer). The exercise goal for all participants is to achieve 10 sets of 60 second bouts of arm cycling at 90% of their PPO (as determined in baseline testing), separated by 60 seconds of active recovery.

Further details regarding the supervised and unsupervised workouts are explained below.

(A) Supervised exercise sessions: the trainer will meet the participant at their home for each supervised exercise session. Prior to exercise, the trainer will measure/record the participant's heart rate and blood pressure. In addition, the trainer will make sure that there haven't been any recent changes in health or medical status (please see "Exercise Training Intake Form" in the "Supporting Documentation" section).

The trainer will guide the participant through a warm-up and stretching routine prior to exercising (approximately 10 minutes). The participant will be familiarized with the same Borg and Wheel RPE scales used during Visit 1, and the Feeling Scale (please see "Feeling Scale" in the "Supporting Documentation" section). The Feeling Scale (-5 very bad to +5 very good) is commonly used to measure affective response during exercise.

The trainer will prescribe individualized work and rest phases based on their PPO from their maximal aerobic test. In order to reach the HIIT goal mentioned above, the trainer will hold participants at 90% PPO as a constant target intensity to start, shortening the work phase (e.g. 10-15 seconds), and if necessary, lengthening the recovery phase (e.g. 75-90 seconds). These ramping parameters will be progressed and documented by the trainer for each session. The trainer will determine when to change their work and rest parameters based off of heart rate and self-reported RPE.

At the end of each session, the trainer will measure/record the participant's heart rate and blood pressure again. Power output and heart rate data is automatically stored in the bike computer during each exercise session. After each session, the data will be transferred to a study iPad/laptop via USB and then deleted from the device. These measures are collected to evaluate adherence to the prescribed HIIT intensities.

(B) Unsupervised exercise sessions: participants will be asked to repeat the same HIIT protocol they performed during the previous supervised session. The trainer will provide written directions for their convenience. Participants will be instructed to wear the heart rate monitor so that during the next supervised exercise session, the trainer will be able to retrieve/collect the data to store on one of our study devices for future analysis. The heart rate data as well as power output data will automatically be stored on the device in the same manner as during the supervised sessions. At the next supervised session, the trainer will retrieve the data from the device.

Visit 2

After completing the 6-week HIIT program, participants will be scheduled for a second/final lab visit. Visit 2 will be ideally scheduled within one week of finishing the 6-week HIIT program, but to provide scheduling flexibility, participants have up to two weeks to complete their second visit. We will try to schedule the follow-up exercise testing around the same time of day as Visit 1. Participants will complete the same exercise testing protocol that was completed in Visit 1. Participants will also complete the NRS, WUSPI, POMS and SF-36 WW questionnaires from Visit 1. Participants will be asked to complete a survey regarding their satisfaction of the HIIT program using the Physical Activity Enjoyment Scale (PACES). Participants will be provided with an open-ended questionnaire to discuss their feelings about HIIT, likelihood to continue, and what would be needed in terms of support to help them (or others like them) to keep doing HIIT. Activity monitors will be removed from the subject and wheelchair.

*Please note: some participants take longer than others to finish questionnaires; to decrease burden, participants will be allowed to complete the questionnaires over the duration of the first lab visit and the first home visit (for baseline measures) and last home visit and second lab visit (for post-trial measures).

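### The activity baseline starts straight after maximal arm testing and has no minimum length, so the measured change in activity may be imprecise and biased in a direction that cannot be known in advance

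*Protocol*

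**What the plan says.** Under Visit 1: Baseline Visit, the protocol describes an incremental arm test that continues "until the participant can no longer continue, or until their respiratory exchange ratio exceeds 1.15". After a rest of at least 20 minutes comes a power test in which "participants will crank as hard and as fast as they are able to for the last 30 seconds". Participants are then introduced to the training: "They will be able to use the ergometer in the lab to try out a brief HIIT protocol". This last step is offered, not required.

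Monitors are issued only after that (Activity Monitor Data Collection): "After the participants are introduced to the training, they will be given the two activities monitors". They are a wrist accelerometer and a gyroscope on the wheelchair wheel, supplied to serve aim 5 when equipment is available. On wear, "Participants will be instructed to wear the activity monitor at all times as tolerated", with exceptions for bathing and swimming.

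The same section defines the baseline: "The baseline period of activity collection will be the time after the first study visit" at the hospital, "until the first in-home training session occurs". Its end therefore depends on the 6-Week HIIT Protocol section: "The first exercise visit will be tentatively scheduled within one week of the first study visit". No minimum gap is given.

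The Overview lists change in activity levels as an additional objective. The SAP text available for this review names a paired t-test for the pre/post capacity measures, which it calls primary, and does not mention activity.

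**The concern.** The baseline is set by the booking diary. Nothing stops the first session from being booked the day after Visit 1, which leaves no complete day of baseline. A Monday visit with a Wednesday session leaves one complete day and no weekend.

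Whatever its length, the window opens with the hours after two maximal arm efforts in untrained people, and the monitors record arm and wheel movement. The protocol's own instructions before testing rule out strenuous activity for the preceding 24 hours, so it accepts that exertion can carry over for about a day. The hours after the tests nevertheless count as usual activity.

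Three features raise the stakes for this objective:

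- No control group is described, so error in the baseline passes directly into the estimated change.
- The PASIPD is completed at Visit 1 but is not among the questionnaires listed for Visit 2. On the supplied text, the monitors are the only repeated measure of activity.
- Baseline days that were not recorded cannot be recovered once training has begun.

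**Working it through.** The documents give no variance, sample size or expected change for activity, so there is no planned figure to reproduce. What follows is an illustration on stated assumptions.

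**Inputs from the protocol.** Start: end of Visit 1. End: first home session. Gap: tentatively up to one week, no lower limit. Sessions: ideally three per week on alternate weekdays.

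**Assumed inputs (not in the documents).** Within-person day-to-day CV of 35% (range 25% to 50%); independent days; a shift of 20% on the first day (range 10% to 30%), in either direction.

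**Step 1: precision of one participant's baseline mean.** SE = CV / √d for d days.

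| Days d | CV 35% | CV 25% to 50% |
|---|---|---|
| 1 | 35 / √1 = 35% | 25% to 50% |
| 3 | 35 / √3 = 20.2% | 14.4% to 28.9% |
| 4 | 35 / √4 = 17.5% | 12.5% to 25% |
| 6 | 35 / √6 = 14.3% | 10.2% to 20.4% |

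These are per participant. The error in a group mean falls with the number monitored, which the supplied text does not give.

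**Step 2: effect of an unusual first day on the baseline mean.** Shift = s / d.

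| Days d | s = 20% | s = 10% to 30% |
|---|---|---|
| 1 | 20% | 10% to 30% |
| 3 | 6.7% | 3.3% to 10% |
| 6 | 3.3% | 1.7% to 5% |

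This treats the test day as a full day. Monitoring starts only after the visit, so in a multi-day window the partial test day would weigh less than shown.

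**Step 3: apparent change when true activity is constant.** If day 1 is 20% low, the apparent change is 1 / (1 − 0.20/d) − 1. If day 1 is 20% high, it is 1 / (1 + 0.20/d) − 1.

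| Days d | Day 1 low (fatigue) | Day 1 high (reactivity) |
|---|---|---|
| 1 | +25.0% | −16.7% |
| 3 | +7.1% | −6.2% |
| 6 | +3.4% | −3.2% |

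**Step 4: can a minimum fit the existing one-week target?** Leave out the test day and ask for four complete days with a weekend day:

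| Visit 1 | First session | Complete days between | Gap |
|---|---|---|---|
| Monday | next Monday | Tue–Sun, 6 | 7 days |
| Tuesday | next Monday | Wed–Sun, 5 | 6 days |
| Wednesday | next Monday | Thu–Sun, 4 | 5 days |
| Thursday | next Tuesday | Fri–Mon, 4 | 5 days |
| Friday | next Wednesday | Sat–Tue, 4 | 5 days |

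Every weekday visit can meet it, with the session on a weekday and within one week.

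**The case against.** The strongest reply is that the documents do not show a bias, let alone its sign. A reader might infer that fatigue lowers the baseline and so makes activity appear to rise with training. That reading is not supported. No section reports reduced activity after testing, and a new monitor or motivation after the visit could raise early activity and push the change downward. Training weeks also contain post-exertion days, since arm HIIT is planned three times a week. The net difference is unknown, and it depends on whether movement during sessions is counted. This objection stands in full.

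Second, the problem is confined to short windows. At six days the assumed 14.3% error is already below the 17.5% of a four-day minimum, and the first-day shift is about 3%. The documents do not show how often short windows would occur. This also stands, but the rule permits them and nothing guards against them.

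Third, no comparison window is defined, so one cannot say that the baseline will be set against six weeks of all day types. Nor is one week a firm upper limit, because the booking is tentative. Both points are right; the undefined window is itself something to settle.

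Fourth, part of the SAP was not available for this review and might hold valid-day rules or exclude the test day. That cannot be ruled out. Such a rule could discard poor days but could not supply days never recorded.

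Finally, activity is an additional objective measured only when equipment allows, and four days is not a figure from the documents. Hence the modest weight given to the point, and the four days are offered only as an example.

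**Conclusion.** The point holds as a weakness of a stated rule. Followed as written, the plan can yield an activity baseline of a day or less that includes time straight after maximal arm testing and contains no weekend.

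The loss of precision does not depend on which way any bias runs: at a 35% CV, moving from one day to four halves the per-participant standard error (35% to 17.5%). Bias is possible, with its direction unknown. It would be material mainly for baselines of one to three days and small near a full week. All these sizes rest on the assumed CV and first-day shift.

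The reach is limited to the activity objective in monitored participants. The pre/post capacity comparison that the SAP calls primary is untouched, as are the feasibility counts. This is a worthwhile, inexpensive improvement.

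**What to change.** 1. Define baseline as complete calendar days starting the day after Visit 1, leaving out the rest of the test day.
2. For monitored participants, book the first session within the protocol's existing one-week target so that a stated minimum of complete days is recorded, for example four including a weekend day. This is a floor; longer baselines should be kept.
3. Compare baseline with training weeks by matched day type (weekday with weekday, weekend with weekend).
4. State the comparison window and whether movement during training sessions counts towards activity.

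Items 1, 3 and 4 need only analysis wording. Item 2 is scheduling guidance. Its cost is slightly less freedom in placing the first session, and a start constraint that participants without monitors do not share. Dropping the test day removes those hours only: it does not remove fatigue that lasts longer, or reactivity that persists while the monitor is new, so the report should still acknowledge both. The minimum should be set before recruitment, because it cannot be applied afterwards to days that were not recorded.

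### No collection point is stated for PACES, the open-ended HIIT questionnaire or the repeat pain scales in participants who stop early, and baseline pain scales may be completed after maximal testing

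*Protocol*

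**What the plan says.** **End of programme.** Under Visit 2 the protocol states: "After completing the 6-week HIIT program, participants will be scheduled for a second/final lab visit". It continues: "Participants will also complete the NRS, WUSPI, POMS and SF-36 WW questionnaires from Visit 1". PACES and an open-ended questionnaire are listed in the same paragraph; the latter invites views on the training and asks for "likelihood to continue, and what would be needed in terms of support to help them (or others like them) to keep doing HIIT". A closing note allows the post-trial forms to be spread over the last home visit and the second lab visit. Visit 2 is ideally within a week of finishing, but "participants have up to two weeks to complete their second visit".

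**Who is enrolled.** Under Visit 1: "Participants will be considered enrolled in the study after they have signed the informed consent document".

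**Baseline order.** The Visit 1 section starts the exercise tests only once every study questionnaire is done. The note at the end of Visit 2 says that, to reduce burden, "participants will be allowed to complete the questionnaires over the duration of the first lab visit and the first home visit".

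**Recall periods.** In the Visit 1 questionnaire list, the NRS asks about the last 24 hours and the WUSPI about the last week.

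**Analysis.** The SAP plans means and standard deviations, or medians and ranges, for all variables. It plans counts of sessions completed and of sessions at target intensity for feasibility, and a paired t-test for the physical capacity measures.

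**The concern.** Acceptability is half of the question in the study title. People who give up the programme are well placed to say whether they would continue and what support they would have needed, yet the stated collection points come only at the end. Session counts show that someone stopped, not why. Pain raises the same issue: if arm pain led a participant to stop, no later NRS or WUSPI is planned for that person in the available text. No denominator is stated for these summaries, so a reader could take them as describing everyone enrolled.

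The second issue is the baseline itself. If a pain scale is answered after two maximal arm tests and a HIIT try-out, pain caused by testing can enter the value against which the post-training score is read.

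**Working it through.** There is no planned figure to reproduce: the available text gives no sample size, dropout rate or expected score for these scales. The check is a comparison of sections and some calendar arithmetic.

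**1. Collection points against the enrolled group.**

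| Measure | Where collected | Can it include early stoppers? |
|---|---|---|
| PACES, open-ended questionnaire | Last home visit or Visit 2 | No point stated |
| Repeat NRS, WUSPI, POMS, SF-36 WW | Last home visit or Visit 2 | No point stated |
| Session counts (SAP) | Throughout training | Yes |
| Feeling Scale (supervised sessions) | Introduced before exercise; recording times not stated | Possibly |

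Enrolment begins at consent and Visit 2 follows completion of the programme, so the two groups differ by whoever stops in between.

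**2. What is left undetermined.** Let q be the share of enrolled participants who stop early and p the share of those reaching the end who give a favourable answer, for example that they would be likely to continue. Early stoppers could all answer unfavourably or all favourably, so the share among all enrolled lies between (1 − q)p and (1 − q)p + q. The width is q, whatever p is, and p itself always lies inside the interval, so bias is possible but not implied. The documents give neither term. Purely as an illustration, assume p = 80%:

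- q = 10%: 0.9 × 80 = 72%, up to 72 + 10 = 82%
- q = 20%: 0.8 × 80 = 64%, up to 64 + 20 = 84%
- q = 30%: 0.7 × 80 = 56%, up to 56 + 30 = 86%

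These are not estimates for this trial.

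**3. Baseline recall.** Let d be the number of days from Visit 1 to the first home visit, tentatively within one week under the 6-Week HIIT Protocol. A form with an r-day recall covers the test day when d ≤ r.

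- WUSPI, r = 7: covered for every d from 0 to 7, so any home visit that keeps to the tentative schedule.
- NRS, r = 1: covered only when d is 0 or about 1.

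**4. Post-training recall.** Count days from the last training session. A WUSPI on day 0 looks back over days −7 to 0, one on day 7 over days 0 to 7, and one on day 14 over days 7 to 14. A post-training score can therefore refer to the last week of training or to a week wholly after it. For Visit 2 the protocol says "Participants will complete the same exercise testing protocol that was completed in Visit 1", but not whether the scales come before or after those tests.

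**The case against.** Several stronger readings are tempting and are not supported.

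- **That acceptability is measured only at the end.** The Feeling Scale is introduced at supervised sessions as a measure of affect during exercise, the protocol overview names positive affect as an attribute of interest, and session counts cover everyone who trains. The gap concerns the named questionnaires.
- **That early stoppers are never asked.** Part of the SAP document, the supporting forms and the numbered aims were not available, and a route could be stated there. What can be said is that the available text states none.
- **That only fully adherent participants are described.** Visit 2 has no minimum number of sessions and three a week is an ideal. Poor adherers who reach week 6 are not shown to be excluded.
- **That the two baseline instructions flatly contradict each other.** The note can be read as an exception with a stated reason. That is a fair reading, but the Visit 1 text covers every questionnaire and has no cross-reference, so staff could follow either. Even as an exception, the WUSPI recall problem remains.
- **That the remote option for week 6 puts post-training scales before the end of training.** This needs the remote option to be chosen, the last home visit to fall in week 5 and the forms to be answered then. Equipment return and data retrieval make later in-person contact plausible.

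It is also fair to say that people may stop for reasons unrelated to acceptability or pain, in which case the bias could be nil.

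**Conclusion.** The point holds in a limited form and is worth fixing; confidence is medium because some material was unavailable. As written, the PACES, open-ended and post-training pain summaries would describe participants who reach the end of the programme, with no stated denominator. The size and direction of any resulting bias cannot be determined from the documents. The baseline instructions need reconciling: a WUSPI deferred to a home visit within seven days includes the test day, and an NRS only within about one day. This affects only the unknown share of participants who defer those forms, and its net effect on the before-and-after difference is unknown. The timing and order of the Visit 2 scales are a minor matter.

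A reader might infer that a planned test is compromised by these questionnaire gaps. It is not: the paired t-test is specified for the physical capacity measures, and the scales discussed here receive descriptive summaries only.

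**What to change.** 1. **Early stoppers.** Offer the open-ended questionnaire by phone or mail to every enrolled participant who discontinues. Offer PACES, NRS and WUSPI to those who did at least one home session. Report early stoppers separately from completers, with denominators for each. Do not pool pain scores from people who never trained as post-training values.
2. **Baseline.** Reconcile the Visit 1 text with the note under Visit 2, so that NRS, WUSPI and POMS are completed before any exercise test and only the other questionnaires may be deferred. POMS belongs in this group because it asks about feelings and the protocol states no recall period for it.
3. **Minor.** At Visit 2, complete NRS, WUSPI and POMS before the exercise tests. Take post-training scales after the last training session and record the completion date of each. Dating does not remove the variation in the WUSPI window, but makes it visible.

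The cost is a wording amendment, one call or mailing per early stopper, and somewhat more questionnaire burden before testing. For three scales this withdraws the relief that the note was written to give. No new questionnaire, visit or test is needed. If data collection has ended, the denominators, and completion timing where dates exist, can still be reported.
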